5.6.2 Adverse Events

All verbatim AE terms will be mapped to MedDRA thesaurus terms, and AE severity will be graded according to the AE Severity Grading Scale (see Table 8 in Protocol).

For safety analyses, unless otherwise specified, only treatment-emergent AEs will be included in the analyses. Treatment-emergent AEs will be defined as any new AE reported or any worsening of an existing condition on or after Study Day 1 or PDS Day 1 per Table 2 through the completion of the study or until a patient discontinues prematurely. AEs with missing onset date will be considered to be treatment-emergent. AEs with partially missing onset date will also be included as treatment-emergent when the month (if it was recorded) and the year occur on or later than the month and year of the study treatment start date.

Due to limited data collection for the comparator patients before their start of ranibizumab treatment, frequency tables, including patient incidence rates by treatment group, will be provided in the Safety-Evaluable Population grouped according to treatment actually received prior to Week 52 only for the events listed below:

AEs leading to study discontinuation

In addition, SARS-CoV 2 related AEs will be provided in a listing by treatment group.

Frequency tables, including patient incidence rates by treatment actually received prior to Week 52 will be provided in the Safety-Evaluable Population, and in the overall PDS Safety Population from day of 1st loading dose injection for the events listed below:

- Ocular AEs and SAEs
- Non-ocular AEs and SAEs
- AESI defined as follows:
 - An AE considered to be sight-threatening (see Section 5.2.3 of the Protocol)

- Cases of potential drug-induced liver injury that include an elevated ALT or AST in combination with either an elevated bilirubin or clinical jaundice, as defined by Hy's Law (see Section 5.3.5.6 of the Protocol)
- Suspected transmission of an infectious agent by the study drug
- Ocular AESI:
 - Vitreous hemorrhage
 - Endophthalmitis
 - Retinal detachment
 - Conjunctival retraction
 - Conjunctival erosion
 - Conjunctival bleb or conjunctival filtering bleb leak
 - Hyphema
 - Cataract
 - Device dislocation
- AEs leading to discontinuation of study treatment
- Treatment, device or procedure related Ocular AEs and SAEs as determined by the Investigator
- Anti-Platelet Trialists Collaboration (APTC) Events defined as:
 - Non-fatal stroke AEs defined by terms from the conditions associated with central nervous system haemorrhages and cerebrovascular accidents Standardized MedDRA Query (SMQ) (Narrow), ischemic cerebrovascular conditions SMQ (Narrow), and hemorrhagic cerebrovascular conditions SMQ (Narrow) or
 - Non-fatal myocardial infarction AEs defined by terms from the myocardial infarction SMQ (Narrow) or
 - Vascular death (including deaths of unknown cause)
- Deaths
- Intraocular inflammation (according to the Standardization of Uveitis Nomenclature (SUN) classification [Jabs et al. 2005]).

AEs will be tabulated by System Organ Class (SOC) and preferred term (PT), and summarized by AE onset day (pre-implant insertion, \leq 37 days post-implant insertion, \geq 37 days post-implant insertion). Separate summaries will be prepared for ocular events in the study eye and fellow eye.

In addition, the following categories of events will be summarized for the overall PDS Safety Population by refill-exchange interval at the time of the final analysis to assess the temporal relationship of events to the refill-exchange procedure (post-operative

period (day of implant through Day 37), Day 38 through first refill-exchange, first refill-exchange through second refill-exchange, etc.):

- Ocular AEs and SAEs
- Ocular AESI and Serious Ocular AESI
- AEs leading to discontinuation of study treatment (also summarized in the Safety-Evaluable Population at Week 52) and AEs leading to explant
- Treatment or procedure related Ocular AEs and SAEs as determined by the Investigator
- AEs related to medical device deficiencies

Ocular AEs and SAEs within 9 days of intravitreal injection, implant or refill-exchange procedure will also be summarized separately. The 9-day cutoff was selected as patients return to the clinic at Day 7 (± 2 days) after implant surgery, and therefore the same window was selected for the evaluation of safety events after refill-exchanges and intravitreal injections.

Listings of AEs, SAEs, AESIs, AEs leading to early discontinuation of study treatment, AEs related to medical device deficiencies (see Section 5.4.4 of the Protocol), vitreous hemorrhage AEs, explantations, re-implantations and deaths will be provided with study day calculated both relative to randomization date and relative to the date of the PDS implant.

Intraocular inflammation is defined based on selected PTs according to the SUN as anterior uveitis (included iritis, iridocyclitis, anterior cyclitis, anterior chamber cell, flare, and inflammation); intermediate uveitis (included pars planitis, posterior cyclitis, hyalitis, vitritis, vitreous haze); posterior uveitis (included choroiditis, chorioretinitis, retinochoroiditis, retinitis, neuroretinitis, retinal vasculitis); and panuveitis (endopththalmitis); and events which were not otherwise specified (included eye inflammation, uveitis, post procedural inflammation, incision site inflammation, inflammation of wound, ocular vasculitis).

Of note, vitreous hemorrhage data will be presented by the functional grading scale for vitreous hemorrhage (see Protocol Appendix 8) which incorporates impact of vitreous hemorrhage on patient's BCVA. All vitreous hemorrhage data will be presented however for key analyses the focus will be on Grades 3 and 4 as these are clinically relevant when discussing vitreous hemorrhage.

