window) because of an extenuating circumstance, the PDS implant insertion may be postponed once for approximately 4 weeks following consultation with the Medical Monitor. If following consultation, the patient will receive an additional intravitreal ranibizumab 0.5 mg injection at the next scheduled Q4W study visit, and will then have the PDS implant (pre-filled with ranibizumab 100 mg/mL) surgically inserted 1-14 days after the intravitreal injection and within the same visit window.

After randomization (Day 1) and until the Week 56 visit (i.e., the comparator-controlled study treatment phase), patients randomized to the comparator arm who meet specific clinical criteria (development of CI-DME or PDR/ASNV; Section 4.3.2.3 of the Protocol) per Investigator assessment can be treated with supplemental intravitreal ranibizumab 0.5 mg injections. The Protocol criteria must be met for the first supplemental intravitreal ranibizumab treatment; subsequent supplemental treatments in the comparator arm can be done per Investigator discretion.

After the Week 64 visit (i.e., the PDS extension phase), comparator arm patients with the PDS implant who meet specific clinical criteria (development of CI-DME or PDR/ASNV) per Investigator assessment can receive supplemental treatment with intravitreal ranibizumab 0.5 mg injections per Investigator's discretion at any non-refill-exchange study visit during the study (see Section 4.3.2.3 of the Protocol).

In the PDS arm, all AEs will be collected after initiation of the first loading dose post-randomization.

In patients randomized to the comparator arm, prior to study drug initiation (either as a supplemental treatment prior to Week 60 or a loading dose), only the following AEs will be collected:

- Serious adverse events (SAEs) caused by a protocol-mandated intervention
- Severe acute respiratory coronavirus 2 (SARS-CoV-2)-related (due to viral infection or vaccine administration) AEs
- AEs leading to study discontinuation

After study drug initiation, all AEs will be collected.

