5.6 SAFETY ANALYSES

Safety will be assessed through descriptive summaries of AEs, ADEs, ocular assessments, and ADAs to ranibizumab. Clinically significant laboratory abnormalities and clinically significant vital sign abnormalities will be reported as AEs and evaluated as part of the AE assessments.

Safety data will be summarized for the Safety-Evaluable Population at the time of the primary analysis through Week 52 and for the PDS Safety Population through the end of the study at the time of the final analysis (see Section 4) unless otherwise specified.

Safety summaries and listings in the Safety-Evaluable Population and in the PDS Safety Population will include data collected on or after Study Day 1 and PDS Day 1 respectively, which are defined as follows:

Table 2 Planned Safety Analyses

Population	Group	Data to be included in the analysis
Safety-Evaluable Population	PDS arm	Day of 1 st loading dose injection (Study Day 1) to Week 52 at the primary analysis
Safety-Evaluable Population	Comparator arm	Day of randomization (Study Day 1) to Week 52 at the primary analysis
PDS Safety Population	PDS arm	Day of 1st loading dose injection (PDS Day 1) through EOS at the final analysis
PDS Safety Population	Comparator arm	Day of 1st loading dose injection (PDS Day 1) (expected at the Week 60 visit) through EOS at the final analysis

CCOD = Clinical Cut-off date; EOS = End of Study; PDS =Port Delivery System with ranibizumab

For patients randomized to the comparator arm, only key safety events (SAEs from Protocol mandated interventions, SARS-CoV-2 related AEs, and AEs leading to study discontinuation, see Section 5.3.1 of the Protocol) will be collected until study treatment (first administration of intravitreal ranibizumab 0.5 mg either as a supplemental treatment or a loading dose) is initiated. Upon initiation of study treatment, all AEs will be reported until the patient's final study visit.

5.6.1 Extent of Exposure

Exposure to study treatment (number of study treatments [PDS refill-exchanges, intravitreal ranibizumab loading doses, supplemental intravitreal ranibizumab injections], duration of treatment) will be summarized by treatment group for the study eye in the Safety-Evaluable Population and in the PDS Safety Population according to the

schedule set in Table 2. Summaries will include the number of intravitreal injections prior to implant, and time to implant post randomization.

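### Section 5.6.2 limits by-arm AE tables in the Safety-Evaluable Population to one event class, then orders them for classes largely uncollected in untreated comparator patients

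*SAP*

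**What the plan says.** **First instruction (Section 5.6.2).** Citing limited data collection in comparator patients before ranibizumab, the SAP provides incidence tables in the Safety-Evaluable Population "grouped according to treatment actually received prior to Week 52 only for the events listed below". The list has one entry, AEs leading to study discontinuation. SARS-CoV-2 related AEs go to a listing.

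**Second instruction (next paragraph).** "Frequency tables, including patient incidence rates by treatment actually received prior to Week 52 will be provided in the Safety-Evaluable Population", and also in the overall PDS Safety Population. The list covers ocular and non-ocular AEs and SAEs, AESI and ocular AESI, AEs leading to treatment discontinuation, related ocular AEs, APTC events, deaths and intraocular inflammation.

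**Collection rules.** For the PDS arm, Section 1.2 states: "In the PDS arm, all AEs will be collected after initiation of the first loading dose post-randomization". Comparator patients follow a narrower rule in the same section: "prior to study drug initiation (either as a supplemental treatment prior to Week 60 or a loading dose), only the following AEs will be collected". The three categories are SAEs caused by a protocol-mandated intervention, SARS-CoV-2 related AEs, and AEs leading to study discontinuation. Section 5.6 repeats that only these key events "will be collected until study treatment (first administration of intravitreal ranibizumab 0.5 mg either as a supplemental treatment or a loading dose) is initiated".

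**Denominator and window.** Table 1 places every randomized comparator patient without an implant before Week 52 in the Safety-Evaluable Population. Table 2 sets that arm's window as "Day of randomization (Study Day 1) to Week 52 at the primary analysis". Comparator loading doses begin at Week 60 (Section 1.2).

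**The concern.** The two paragraphs name the same table type, population and grouping. One restricts the content to a single class and the other does not, so a programmer cannot follow both and the SAP gives no rule for choosing.

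Neither works alone. Taken literally, the first drops by-arm tables of deaths and of SAEs caused by protocol-mandated interventions, although the latter are collected in both arms. The second puts a fully observed PDS column beside a comparator column in which most events could not have been recorded, over a full-arm denominator. Uncollected events would then read as events that did not happen, and PDS would look relatively worse because of the collection rule alone.

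**Working it through.** The SAP states no figure on this point to reproduce. The check is textual, followed by a bound and an illustration.

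**1. Who can contribute events before Week 52.** Comparator loading starts at Week 60, after the Week 52 cut-off. Only supplemental ranibizumab opens full AE collection earlier. All other comparator patients contribute just the three collected categories but remain in the denominator (Tables 1 and 2).

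**2. Which classes are affected.**

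| Affected in comparator patients before ranibizumab | Not or little affected |
|---|---|
| General ocular and non-ocular AEs | AEs leading to study discontinuation |
| SAEs not caused by a protocol-mandated intervention | SAEs caused by a protocol-mandated intervention |
| AE-reported AESI that need no drug or device (vitreous hemorrhage, retinal detachment, cataract) | SARS-CoV-2 related AEs |
| AE-reported intraocular inflammation | Events that presuppose drug or device: related AEs, treatment discontinuations, suspected transmission by study drug, conjunctival and device AESI |
| Non-fatal stroke and myocardial infarction, hence the APTC total | |

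An event in the left column still counts if it also falls in a collected category. Fatal AEs may be captured as study discontinuations; the SAP does not say.

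**3. Bound that needs no assumed rate.** Let k be the number of the roughly 60 comparator patients given supplemental ranibizumab before Week 52. For an affected class, displayed incidence ≤ k/60, apart from events that also fall in a collected category. With k = 0 it is 0. The PDS column has no such ceiling.

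**4. Illustration only.** The SAP gives neither the share s given supplemental ranibizumab nor any AE incidence p. Assume s = 0.15 to 0.45 (k = 9 to 27), a start uniform over 52 weeks, and a constant hazard equal in treated and untreated patients:

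- λ = −ln(1 − p)
- displayed = s × (1 − p/λ)
- displayed/true = s × (1 − p/λ)/p

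At p = 0.30, λ = 0.3567, p/λ = 0.841 and (1 − 0.841)/0.30 = 0.530.

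| True p | s | Displayed | Patients of 60 |
|---|---|---|---|
| 0.30 (18 patients) | 0.15 | 2.4% | 1.4 |
| 0.30 | 0.30 | 4.8% | 2.9 |
| 0.30 | 0.45 | 7.2% | 4.3 |
| 0.02 (1.2 patients) | 0.15 | 0.15% | 0.1 |
| 0.02 | 0.45 | 0.45% | 0.3 |

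The factor (1 − p/λ)/p is 0.502 at p = 0.02, 0.509 at 0.10, 0.530 at 0.30 and 0.557 at 0.50. So displayed/true is close to s/2: about 0.08 at s = 0.15 and 0.23 to 0.25 at s = 0.45. If every treated patient started at Week 4, the ratio would rise to 0.92 to 0.95 times s.

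**The case against.** **The second paragraph may mean the PDS arm.** It ends with a clause dating the tables from the first loading dose. If that clause governs both populations, comparator patients drop out before Week 60, in line with the first paragraph. The onset strata point the same way: "AEs will be tabulated by System Organ Class (SOC) and preferred term (PT), and summarized by AE onset day (pre-implant insertion", then up to and beyond 37 days after it, and comparator patients in this population have no implant before Week 52. This suggests intent but does not settle the text. The sentence structure ties the clause to the PDS Safety Population, nothing says PDS arm only, and an empty comparator column contradicts Table 2's comparator row. The general Day 1 rule in Section 5.1 does not help either, since untreated patients still count from randomization.

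**The cross-reference is weak support.** A later list in 5.6.2 reads "AEs leading to discontinuation of study treatment (also summarized in the Safety-Evaluable Population at Week 52) and AEs leading to explant". It shows that one item of the second list is meant for this population. That class presupposes study treatment, so it does not prove a comparator column is intended for general AEs. This is fair.

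**The limitation is disclosed and the analysis is descriptive.** Both are true. Slit-lamp, ophthalmoscopy and IOP summaries in Section 5.6.6, and the BCVA comparisons, also give partial ocular information across arms. The remaining gap is mainly non-ocular AEs, non-fatal stroke and myocardial infarction, and ocular AEs those examinations do not tabulate.

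**The equal-hazard assumption is doubtful.** Supplemental treatment follows CI-DME or PDR/ASNV, and the SAP's introduction names vitreous hemorrhage as a complication of progression. For that class the illustration may understate capture. The k/60 ceiling does not depend on it.

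**Conclusion.** The contradiction stands. As written, the second instruction would understate comparator incidence for the affected classes. The firm statement of size is the k/60 ceiling, which follows from the collection rule and the denominator. The illustrative range, about 8% to 25% of true incidence displayed, rests on the assumed share, timing and hazard; it shows direction and is not an estimate.

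The consequence is limited to the reading of descriptive safety tables: no AE test or risk difference is planned, and no efficacy conclusion changes. It should be corrected, but it does not threaten the trial's main result.

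**What to change.** Reconcile the two paragraphs of Section 5.6.2 by stating which Safety-Evaluable tables carry a comparator column:

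- **Classes collected in both arms from Day 1:** keep cross-arm columns. Expressly retain deaths by arm, and state or cross-refer to how comparator deaths before ranibizumab are captured.
- **All other classes:** show the PDS arm. Show comparator AEs only among patients given ranibizumab, counted from first dose on that denominator, with a footnote on the collection limit. This is a post-randomization subset selected for progression, so the footnote should also say that it is not comparable with the PDS column.

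Section 5.5.5 already summarizes how many comparator patients in this population receive supplemental ranibizumab, so the denominator needs no new data.

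The cost is SAP wording and table shells. The price is that no full-arm comparator percentage appears for classes not collected before ranibizumab, and the comparator denominators are small (9 to 27 of 60 under the assumed shares).

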Patients randomized to the PDS arm will receive at least two loading doses with intravitreal ranibizumab 0.5 mg injections, administered at Day 1 and Week 4 visits. The first loading dose must be administered after the conclusion of the randomization visit assessments. At Week 4, patients must complete a pre-implant visit prior to the implant insertion surgery. Both visits must be completed within the Week 4 window and the PDS implant (pre-filled with ranibizumab 100 mg/mL) will be surgically inserted 1-14 days after the second loading dose (e.g., if the patient receives the second loading dose at Day 28 (Week 4), implant insertion surgery must occur no earlier than Day 29 and no later than Day 35). Patients will receive PDS implant refill-exchange procedures (ranibizumab 100 mg/mL) at Weeks 40, 76, 112, and Q36W thereafter (Visit Z refill-exchange visit) until the end of the study.

Patients in the PDS arm who meet specific clinical criteria (development of CI-DME or PDR/ASNV) per Investigator assessment can receive supplemental treatment with intravitreal ranibizumab 0.5 mg injections per Investigator's clinical judgment at any non–refill-exchange study visit during the study post implant (see Section 4.3.2.3 of the Protocol).

Patients randomized to the comparator arm will undergo study visits every 4 weeks (Q4W) for observation and comprehensive clinical monitoring. Beginning at Week 60, patients will receive two loading doses with intravitreal ranibizumab 0.5 mg injections, administered at the Week 60 and Week 64 visits. At Week 64, patients must complete a pre-implant visit prior to the implant insertion surgery. Both visits must be completed within the Week 64 window and the PDS implant (pre-filled with ranibizumab 100 mg/mL) surgically inserted 1-14 days after the Week 64 intravitreal injection. Patients will undergo a refill-exchange procedure with ranibizumab 100 mg/mL at Week 100 and Q36W thereafter (Visit Z refill-exchange visit) until the end of the study.

If PDS implant insertion surgery cannot be completed within the required timeframe (1-14 days after intravitreal ranibizumab 0.5 mg injection and within the study visit

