4. ANALYSIS SETS

The following populations are defined:

Table 1 Analysis Sets

Population	Definition
ITT Population	All patients who are randomized. Patients will be grouped according to treatment assigned at randomization.
Safety-Evaluable Population	All patients who receive any study treatment, and patients randomized to the comparator arm under observation, grouped according to treatment actually received prior to Week 52. In the PDS arm, the population includes all patients randomized to PDS receiving at least one loading dose, or any patient who received the PDS implant prior to Week 52. In the comparator arm, the population includes all patients randomized to the comparator arm who did not receive the PDS implant prior to Week 52.
PDS Safety Population	All patients who receive the PDS implant, including patients in the comparator arm who cross over to receive PDS at Week 64. Analyses on this population will only include data after first loading dose. Patients will be grouped according to treatment actually received prior to Week 52 (i.e. patients receiving PDS prior to Week 52 are grouped to the PDS arm, and patients receiving PDS after Week 52 are grouped to the comparator arm).
PDS PK Population	All patients who are randomized with at least one post implant PK sample available and who receive PDS at any time point, grouped according to treatment actually received prior to Week 52, and overall. Analysis is relative to time since implant insertion.

PDS PK Evaluable Population	All patients in the PDS PK Population excluding patients receiving intravitreal injections of ranibizumab in the study eye post PDS implant (including supplemental treatment) or patients with fellow eye ranibizumab after randomization, or bevacizumab treatment in either eye within 9 months prior to randomization or after randomization, or patients with septum dislodgment. Patients will be grouped according to treatment actually received prior to Week 52, and overall. Analysis is relative to time since implant insertion.
Aqueous Humor PK Evaluable Population	Subset of patients in the PDS PK Evaluable Population with at least one post implant aqueous humor PK sample. Patients will be grouped according to treatment actually received prior to Week 52,and overall.

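### The end-of-study safety percentages in the PDS Safety Population mix risk periods that differ by about 60 weeks, and for non-ocular events, APTC events, deaths and late-period totals no planned table corrects for this

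*SAP*

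**What the plan says.** SAP Table 2 (section 5.6) sets the data window for the PDS Safety Population. For the PDS arm it is "Day of 1st loading dose injection (PDS Day 1) through EOS at the final analysis". For the comparator arm it is "Day of 1st loading dose injection (PDS Day 1) (expected at the Week 60 visit) through EOS at the final analysis".

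Table 1 (section 4) says of this population: "Patients will be grouped according to treatment actually received prior to Week 52". Patients who cross over after Week 52 thus form the comparator group.

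Section 5.6.2 reports adverse events as frequency tables with patient incidence, in the Safety-Evaluable Population "and in the overall PDS Safety Population from day of 1st loading dose injection for the events listed below". Section 5.1 gives counts and percentages as the general summary for categorical data. Section 5.6 specifies no person-time rate, time-to-first-event summary or common follow-up cut for adverse events.

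Two features partly align the risk periods:
- Events are split by onset before implant, up to 37 days after it, and later. The last category has no upper limit. Section 5.6.2.1 uses the same post-implant split for ADEs.
- In 5.6.2, "the following categories of events will be summarized for the overall PDS Safety Population by refill-exchange interval at the time of the final analysis". The categories are ocular AEs and SAEs, ocular AESIs, AEs leading to discontinuation or explant, related ocular events, and device-deficiency AEs.

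Section 5.6.1 tabulates duration of treatment by group but does not use it as a denominator for adverse events.

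**The concern.** A percentage of patients with any event grows with time under observation. If one group is watched about 60 weeks longer than another, its percentage is higher even when the risk is identical. The pooled figure averages two follow-up lengths and describes neither.

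At stake is how the long-term safety of the implant is read. The crossover group could look safer only because it was watched for less time, and the pooled percentage would understate the risk at the longer follow-up. This matters most for event types with no table by time since implant: non-ocular AEs and SAEs, APTC events and deaths. It also matters for the totals after Day 37, which carry the whole difference in follow-up. Ocular AESIs in that later period are a stated safety endpoint (section 1.1.2).

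**Working it through.** **1. The plan's own offset.** Table 2 expects PDS Day 1 at Week 60 in the comparator arm. The schedule in section 1.2 agrees. The PDS arm has loading "injections, administered at Day 1 and Week 4 visits" and refill-exchanges "at Weeks 40, 76, 112, and Q36W thereafter". The comparator arm has loading "administered at the Week 60 and Week 64 visits" and its first refill-exchange at Week 100.
- First loading dose: 60 − 0 = 60 weeks
- Pre-implant visit: 64 − 4 = 60 weeks
- First refill-exchange: 100 − 40 = 60 weeks

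The figure is reproduced. It is the planned difference; postponed implants and dropout will vary it.

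**2. Follow-up.** Section 5 leaves the end of study to the sponsor, so its week T is an assumption. Follow-up is T weeks in the PDS arm and T − 60 in the crossover group.

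**3. Crude incidence under identical risk.** The rates are assumptions, with t in years (weeks / 52). Surgical risk is placed at the start for simplicity. Planned sizes of 100 and 60 (section 3) weight the pooled column.
- Constant risk of 10 per 100 patient-years: 1 − exp(−0.10 t)
- 10% at surgery plus 5 per 100 patient-years: 1 − 0.90 × exp(−0.05 t)
- Pooled: (100 × PDS arm + 60 × crossover) / 160

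| End of study | Follow-up, weeks | Constant risk: PDS / crossover / pooled | Surgical peak: PDS / crossover / pooled |
|---|---|---|---|
| Week 112 | 112 vs 52 | 19.4% / 9.5% / 15.7% | 19.2% / 14.4% / 17.4% |
| Week 148 | 148 vs 88 | 24.8% / 15.6% / 21.3% | 21.9% / 17.3% / 20.2% |
| Week 184 | 184 vs 124 | 29.8% / 21.2% / 26.6% | 24.6% / 20.1% / 22.9% |

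The false difference is 9.9, 9.2 and 8.6 points under constant risk, and 4.8, 4.6 and 4.5 points with the surgical peak. If all the risk were peri-operative, it would vanish.

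**4. Would one person-time rate cure it?** Only under constant risk. With the surgical peak, mean time at risk to first event is (0.90 / 0.05) × (1 − exp(−0.05 t)).
- 112 weeks: 18 × (1 − 0.8979) = 1.84 years; 0.192 / 1.84 = 10.4 per 100 patient-years
- 52 weeks: 18 × (1 − 0.9512) = 0.88 years; 0.144 / 0.88 = 16.4 per 100 patient-years

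Identical risk now looks higher in the crossover group, so the error has changed direction.

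**5. Denominator of the interval tables.** With an end at Week 112, PDS-arm patients pass their second refill-exchange at Week 76. Crossover patients reach their first at Week 100, and their second would fall at Week 136. None of the crossover patients enters the interval after the second refill-exchange. If the whole pooled population were the denominator there, the percentage would shrink by a factor of 100 / 160 = 0.625, assuming planned sizes with everyone implanted and retained. The SAP does not say which denominator applies. For supplemental treatment by refill interval, section 5.4.2.14 does restrict it to patients who could be assessed.

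**The case against.** A reader might infer that delayed implant harms, such as conjunctival erosion or retraction, endophthalmitis, cataract or device dislocation, cannot be tied to any time since implant. The SAP does not support that. All five are ocular AESIs, and 5.6.2 summarizes ocular AESIs by refill-exchange interval. The interval tables also take in all ocular AEs, and so the intraocular inflammation terms. The listings give study day relative to implant. This part of the objection stands, apart from the unstated denominators.

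A second point is that the Safety-Evaluable tables already give PDS-arm incidence to Week 52. If the study ended at Week 112, crossover patients would also have 52 weeks, giving a roughly common window. This helps only at that end date, and the populations differ, because the Safety-Evaluable PDS arm includes patients who were loaded but not implanted.

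Third, the sentence in 5.6.2 refers to the overall population and could mean pooled tables only; separate group columns are inferred from Tables 1 and 2. That is fair, but the pooled percentage still mixes the two windows.

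Fourth, both groups receive the same implant, the summaries are descriptive, and exposure is tabulated by group. All true. Tabulated exposure shows a reader that follow-up is unequal but does not correct the percentages.

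Finally, the 19.4% vs 9.5% example uses the earliest end date tried and a constant risk. It should be read together with the surgical-peak case, where the gap is about half as large.

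**Conclusion.** The point holds in a limited form. The through-end-of-study frequency tables in the PDS Safety Population rest on windows that differ by a planned 60 weeks, and no common cut or time-to-first-event summary is specified. The refill-exchange-interval tables largely deal with this for the ocular, discontinuation or explant, and device-deficiency categories. It remains for non-ocular AEs and SAEs, APTC events, deaths, and the open-ended totals after Day 37, including those for ADEs in 5.6.2.1.

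Under identical risk, the spurious gap between groups is about 4.5 to 10 percentage points in the scenarios shown. That range depends on the assumed end of study (Weeks 112 to 184), the assumed rates and the shape of the hazard.

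It would be wrong to infer that the efficacy comparison or any confirmatory test is biased. The safety summaries are descriptive, and the randomized comparison does not use this population.

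**What to change.** In SAP 5.6.2, for the PDS Safety Population at the final analysis:
- Add Kaplan-Meier cumulative incidence at fixed times since first loading dose, and since implant for ocular AESIs, by group and pooled. The SAP already uses Kaplan-Meier through end of study for the progression endpoints in 5.4.2.3 to 5.4.2.7.
- Restrict any side-by-side group percentages to a common window that both groups reach.
- State that the denominator of each refill-interval table is the patients who enter that interval.
- If exposure-adjusted rates are wanted, give them separately for the post-operative and later periods. A single rate over the whole follow-up is distorted by peri-operative risk.

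The same common-window or Kaplan-Meier approach should cover the late-period ADE totals in 5.6.2.1.

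The cost is SAP wording and a few extra tables from dates already collected. The common-window display uses less of the PDS-arm follow-up, but the Kaplan-Meier estimates retain it. No hypothesis test changes.
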